#### 3.2 Secondary Outcome Measures (SOM):

- a) SOM 1.1: Categorical change (positive, negative, no change) in pre- and post- vaccination state anxiety.
- b) SOM 1.2: Numeric change (mean and 95% CI) in pre- minus post- vaccination state anxiety.
- c) SOM 2.1: Mean injection-site pain scores on the Wong-Baker Faces Pain Scale© at  $\leq 1$  minute following vaccination.
- d) SOM 2.2: Proportion of adolescents reporting an injection site pain score  $\geq 2$ , on the Wong-Baker Faces Pain Scale©,  $\leq 1$  minute following vaccination.
- e) SOM 2.3: Proportion of adolescents reporting an injection site pain score  $\geq 4$ , on the Wong-Baker Faces Pain Scale©,  $\leq 1$  minute following vaccination.
- f) SOM 2.4: Mean injection-site pain scores on the Wong-Baker Faces Pain Scale© at (approximately) 10 minutes following vaccination.
- g) SOM 2.5: Proportion of adolescents reporting an injection site pain score  $\geq 2$ , on the Wong-Baker Faces Pain Scale©, at (approximately) 10 minutes following vaccination.
- h) SOM 2.6: Proportion of adolescents reporting an injection site pain score  $\geq 4$ , on the Wong-Baker Faces Pain Scale©, at (approximately) 10 minutes following vaccination.
- i) SOM 3: Proportion of adolescents reporting positive and negative perceptions about their vaccination experience will be determined for each survey item.

#### 3.3 Exploratory Outcome Measures (EOM):

- a) EOM 1: Proportion of adolescents with presyncope or syncope after vaccination in the intervention and usual care groups using the alternate case definitions for presyncope.
- b) EOM 2: Descriptive results of factors associated with post-vaccination presyncope and syncope using the primary and alternate case definitions for presyncope.

### 4 Study Design

#### 4.1 Study Description

This study is a prospective, randomized clinical trial that will be conducted in adolescents (10 through 14 years of age) receiving at least one recommended intramuscularly administered vaccine to evaluate the efficacy and acceptability of using two different, simultaneously administered interventions that might prevent post-vaccination presyncope, and by extension syncope. The two interventions to be evaluated together are Buzzy®, which is a medical device designed to reduce vaccination pain, and an electronic game. We will evaluate both interventions when administered simultaneously (Buzzy® and electronic game). We will enroll approximately 340 subjects into this study. Eligible adolescents will be randomized (1:1) to either the intervention or control group: 1) intervention (Buzzy® and electronic game); or 2) control (usual care) to assess for acceptability and efficacy. Detailed data will be collected and described from study participants including demographics, medical history, baseline anxiety, and needle phobia. Participants will be observed for 20 minutes following receipt of vaccines and reassessed for post-vaccination anxiety, immediate and subsequent post-vaccination pain (within 1 minute and at 10 minutes), and the occurrence of witnessed syncope or presyncope, and presyncope symptoms as rated by the modified BDRI. For the primary objective, we will assess the efficacy of the intervention to decrease presyncope symptoms or signs as compared to usual care. For the secondary

objectives we will assess the pre- and post-vaccination anxiety score, the immediate post-vaccination injection-site pain score, and the acceptability of the intervention. For the exploratory objectives we will assess the efficacy of the intervention to decrease presyncope symptoms or signs as compared to usual care using alternate case definitions for presyncope and we will assess factors associated with post-vaccination presyncope.

#### 4.2 Study Interventions

##### a) Buzzy® and Electronic Game Intervention

Participants randomized to Buzzy® and the electronic game will apply or have Buzzy® applied by a member of the study team. Buzzy® XL Healthcare Professional will be applied as described in the package insert on the deltoid vaccination site for 30-60 seconds. Then, the Buzzy® will be moved proximal to the injection site keeping Buzzy's® switch/head toward the brain or spine during injection. The procedures for applying Buzzy® are consistent with the procedures on the package insert. If vaccines are given in more than one arm, Buzzy® will be placed on both arms with the assistance of the study coordinator. Buzzy® will be removed from the vaccination site(s) following vaccination. The start and stop time of Buzzy® placement will be recorded. If more than one vaccination is given in a single arm only one Buzzy® device will be applied per package instructions.

For the electronic game, participants will be instructed to select a game from a prepopulated list of games on a tablet provided by the study team. The game will be played for a minimum of 3 to 5 minutes prior to vaccination, throughout the procedure and for a minimum of 1 minute and up to 15 minutes after vaccination.

Although preferable for participants to remain in the same exam room during the post-vaccination observation period, participants may have to shift rooms during the post-vaccination observation period. The participant will be provided with the guidance (derived from the Advisory Committee on Immunization Practices (ACIP) General Best Practices Guidelines for Immunization) that they may choose to sit or lie down during the post-vaccination wait period. Movement from room to room or if the patient decides to stand should be noted by the study staff. No instruction will be provided to the participant regarding sitting or standing unless the participant starts to exhibit signs of presyncope.

##### b) Control Group

This intervention group will receive usual care during vaccination. Usual care will include not receiving the Buzzy® and electronic game combination intervention and will also consist of the patient waiting in the exam room for 20 minutes post-vaccination. The participant will also be provided with the ACIP guidance that they may choose to sit or lie down during the post-vaccination wait period. Although preferable for participants to remain in the same exam room during the post-vaccination observation period, participants may have to shift rooms during the post-vaccination observation period. Movement from room to room should be noted by the study staff.

#### 4.3 Sample Size and Power Estimation

The study has approximately 82.0% power to reject the null hypothesis of no difference in the proportion of adolescents with presyncope or syncope after vaccination in the intervention (vibration and cool pack device [Buzzy®] and an electronic game) group compared to the control (usual care) group based on a two-side alpha 0.05 chi-square test with N=160 per group. This assumes that the proportion of adolescents with presyncope or syncope after vaccination will be 25% in the control group and 2-fold lower (12.5%) in the intervention group. This assumption is based on a review of the literature and expert opinion. We plan to enroll approximately 340 adolescents for this study with the assumption of a 5% drop out rate, thus providing at least 160 subjects per group to have approximately 82% power.

#### 4.4 Randomization

Participants will be randomized (1:1) to receive either Buzzy® and electronic game or the control using a permuted block randomization scheme. A minimum of 170 participants will be enrolled in the intervention group and 170 in the control group. The project statistician at Duke University will generate randomization schemes, which will be uploaded to REDCap. The randomization schedule will not be available to the study staff, so the next randomization allocation will not be known before randomization occurs. Following confirmation of study eligibility criteria during Visit 1, participant randomization will be through REDCap with treatment allocation recorded on the CRF.

#### 4.5 Blinding

Study staff and subjects will not be blinded to treatment arm assignments.

#### 4.6 Definitions

##### a) Presyncope

The case definition of presyncope was based on review of the literature, an amended Blood Donations Reactions Inventory (BDRI).

Primary definition: Sudden onset of one or more of the following symptoms (reported as “a little bit”, “somewhat” or “a lot”) or signs during the post-vaccination observation period in the clinic:

##### Symptoms

- Feeling like you might “pass out” or faint
- Feeling dizzy, like the room is spinning
- Feeling weak
- Feeling like your face is getting red and warm (or hot), like blushing or flushing
- Noticing any change in your vision, like spots or flickering lights, tunnel vision, or loss of vision
- Experiencing ringing in your ears, decreased hearing, or sounds seem far away
- Feeling lightheaded
- Feeling like your heart is beating fast or hard or pounding
- Feeling hot or sweaty
- Feeling cold or “clammy”
- Feeling like you are breathing fast or hard
- Feeling like you might throw up (nausea)

##### Signs

- Pallor
- Sweatiness
- Facial flush
- Decreased interactivity (decreased level of arousal or responsiveness)

##### AND

- Not syncope
- Not due to another cause
- Not clearly present at baseline

In exploratory analyses we will employ two alternate case definitions for presyncope.

Alternate definition 1: Sudden onset of one or more of the above symptoms (reported as “somewhat” or “a lot”) or signs during the post-vaccination observation period in the clinic.

Alternate definition 2: Sudden onset of one or more of the following symptoms limited to feeling like you might pass out, dizziness, weakness, or lightheadedness symptoms (reported as “a little bit”, “somewhat” or “a lot”) or signs during the post-vaccination observation period in the clinic.

b) **Syncope**

Syncope (fainting) that occurs in an otherwise healthy person after receipt of a vaccine or during venipuncture is usually attributed to vasovagal syncope, and may occur alone (simple syncope) or may be associated with tonic-clonic movements (convulsive syncope, anoxic seizure). For the purposes of this study, we have defined syncope as: Any sudden and brief loss of consciousness or postural tone after vaccination from which recovery is spontaneous and is not attributed to another cause (e.g., anaphylaxis). For purposes of this study, cases counted as syncope must occur during the post-vaccination observation period.

## 5 Statistical Considerations / Parameters of Analysis

### 5.1 Data Collection and Storage

Data will be handled according to the Duke Vaccine and Trials Unit SOP (DVTU M010) and captured on paper CRFs and entered into the REDCap database. All data for this study will reside on a secure Duke server maintained by Duke Health Technology Solutions (DHTS). A database will be developed and a dataset without personal identifiers will be made available to the CDC for analysis purpose. All analyses will be performed using SAS version 9.4.

### 5.2 Analytic Issues

No adjustments will be made to the alpha level (two-sided alpha=0.05) for the study objectives described below.

The primary and exploratory objective analyses will be performed in the Modified intent-to-treat (mITT) and Per-protocol populations, or only the mITT population if no subject is excluded from the per protocol population. No adjustments will be made to the alpha level (two-sided alpha=0.05) for the study objectives described below.

## 6 Analysis Populations

### 6.1 Modified Intent-to-treat (mITT):

Defined as those subjects who are enrolled, randomized into the study, and received an intramuscular vaccine.

### 6.2 Per-Protocol population:

Defined as those subjects who are randomized, have received at least one dose of an intramuscularly administered vaccine, have completed all study procedures, and have no protocol violations that are likely to affect the objectives.

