Visit 1, Study Day 1 Clinic Visit Post Vaccination Assessments

- Complete the Wong-Baker Faces Pain assessment for **each arm** an injection is given in (immediately after withdrawal of the needle after the last vaccination within 1 minute (up to 3) after last injection and at 10 (up to 15) minutes after the last vaccination). If multiple injections are given in the same arm only 1 Wong-Baker Faces Pain assessment will be performed for that arm at 1-3 minutes and 10 (up to 15) minutes after the last injection.
- Complete the presyncope symptoms assessment modified BDRI (15 (up to 20) minutes post vaccination)
- Complete the state anxiety assessment (20 [up to 25] minutes post vaccination)
- Complete the acceptability assessment (20 [up to 30] minutes post vaccination)

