7.12 Presyncope and Syncope

At 15 minutes (up to 20 minutes) following vaccination, study participants will complete the BDRI. During the 15 minute (up to 20 minute) observation period, research staff

will also record any observed signs (pallor, sweating, facial flush or decreased interactivity) or spontaneous subject reports of symptoms of witnessed presyncope as described in Section 4.1. Subjects who developed post-vaccination syncope as described in Section 4.2 regardless of presyncope are classified as having syncope. Usual clinical care will be provided to any subject who develops presyncope or syncope.

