## 8 Analysis of study objectives

### 8.1 Primary Objective (PO1)

To assess if simultaneous use of a vibration and cool pack device (Buzzy®) and an electronic game before and during intramuscular vaccination will reduce risk for presyncope or syncope after vaccination in adolescents. This information is collected in CRF forms: “Buzzy® Form”, “Electronic Game Form”, “Presyncope or Syncope Form (EVENT FORM)”, and “Post Vaccination Questions” (Modified BDRI (PostVax)). The proportion of adolescents with presyncope or syncope as determined by the modified BDRI or witnessed presyncope or syncope after vaccination will be compared between the control and intervention groups using a chi-square test.

- *Research hypothesis: The Buzzy® and electronic game intervention will be at least 50% effective at reducing risk for post-vaccination presyncope or syncope compared with control.*  
This objective will be assessed using a chi-square test with the alpha level set at 0.05 (2-sided).

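### Presyncope or syncope can itself put a child outside the per-protocol set, with one extra route in the intervention arm, so the per-protocol comparison can be biased

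*SAP*

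**What the plan says.** SAP 6.2 and Protocol 8.2.1 define the per-protocol population in the same terms: randomised children given at least one intramuscular vaccine who "have completed all study procedures, and have no protocol violations that are likely to affect the objectives". Neither document lists the disqualifying violations or says whether short game play is one. Neither says who decides, when, or with what knowledge of the outcome.

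The procedures to be completed are these:

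- **Intervention arm.** Table 1 in Protocol 7.1 lists the device-and-game intervention (or usual care) in its procedure column. SAP 4.2 a) and Protocol 7.9.1 require the game to be played before vaccination, then "throughout the procedure and for a minimum of 1 minute and up to 15 minutes after vaccination".
- **Control arm.** Usual care, which "will also consist of the patient waiting in the exam room for 20 minutes post-vaccination" (SAP 4.2 b); the same in Protocol 7.9.2).
- **Both arms.** Pain scores at 1 (up to 3) and 10 (up to 15) minutes and state anxiety at 20 (up to 25) minutes (Protocol 7.1). Protocol 7.12 adds: "At 15 minutes (up to 20 minutes) following vaccination, study participants will complete the BDRI".

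The primary outcome is presyncope or syncope "as determined by the modified BDRI or witnessed presyncope or syncope after vaccination" (SAP 8.1), so a witnessed event counts even if the BDRI is never filled in. Presyncope requires at least one listed symptom, of sudden onset, "or signs during the post-vaccination observation period in the clinic" (SAP 4.6 a)).

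On populations, SAP 5.2 says: "The primary and exploratory objective analyses will be performed in the Modified intent-to-treat (mITT) and Per-protocol populations". Alpha is 0.05 two-sided without adjustment, and neither population is called the main one. mITT asks only for enrolment, randomisation and an intramuscular vaccine (SAP 6.1). The trial is open label (SAP 4.5).

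**The concern.** Membership of the per-protocol set depends on conduct after randomisation, and the primary outcome can change that conduct. A child who turns faint may put the tablet down, or be in no state to complete a timed questionnaire. Read literally, that child has not completed every procedure and leaves the set because of the event being counted.

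The routes are not the same in the two arms. Missed assessments can remove cases from either arm. The post-injection play requirement exists in the intervention arm only, and it adds a way to lose cases there. Losing cases from one arm lowers that arm's event rate with no real effect behind it. If mITT and per-protocol then disagreed, the plan would give no means of telling efficacy from selection and no rule for which result decides the primary objective.

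**Working it through.** **1. The plan's own figure.** Inputs from SAP 4.3: 25% in control, 12.5% in intervention, 160 per arm, two-sided 0.05 chi-square. With the pooled rate 0.1875:

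power = Φ{[0.125·√160 − 1.96·√(2·0.1875·0.8125)] / √(0.25·0.75 + 0.125·0.875)} = Φ{(1.581 − 1.082)/0.545} = Φ(0.916) = 82.0%.

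This reproduces the stated figure. It applies to an analysis without this exclusion, as in mITT.

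**2. Which cases the extra route can reach.** Required play after vaccination is 1 minute; play up to 15 minutes is permitted, not required. A child who turns faint after the first minute and then stops has met the minimum. The route therefore covers only stopping during the injections or in the first minute, by a child who also qualifies as a case in the post-vaccination observation period. The documents give no onset times.

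**3. Effect on the rate.** Let *s* be the share of intervention cases lost by this route. It is not in the documents and is an assumption. The observed rate becomes p(1 − s)/(1 − p·s). With no true effect, p = 0.25, so 40 cases are expected among 160:

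- s = 5% (2 cases): 0.2375/0.9875 = 24.1%; relative risk 0.241/0.25 = 0.96.
- s = 10% (4 cases): 0.225/0.975 = 23.1%; relative risk 0.92.

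**4. Effect on the test.** 400,000 simulated trials per scenario, uncorrected chi-square, 160 per arm before exclusions, no true effect, loss in the intervention arm only:

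| Share lost | Chance of a false significant benefit |
|---|---|
| 0% | 2.5% |
| 5% | 3.9% |
| 10% | 5.9% |
| 20% | 12.8% |

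At s = 10% the total two-sided rejection rate is 6.8%. At the planned effect (25% vs 12.5%, 20 expected intervention cases), losing 10% (2 cases) moves the relative risk from 0.50 to 0.46 and the apparent power to 89%.

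**5. Loss in both arms.** The missed-assessment route is open to both, so the same simulation was run with cases lost in each:

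- Equal loss, 10% or 20% in each arm, no true effect: the false-benefit chance stays at 2.5%.
- 20% lost in control and 10% in intervention: false benefit 0.8%, false harm 6.3%. The tilt reverses.

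**6. Distance to a changed conclusion.** Starting from exactly 40/160 in each arm, 18 intervention cases must be removed before p falls below 0.05 (p = 0.041).

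**The case against.** The case for leaving the text alone has several parts.

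- *The rule applies to both arms.* This stands. A control child with a witnessed event who then misses the BDRI or the anxiety score is also a case who leaves. A reader might infer that only intervention cases can be lost and that the per-protocol result is therefore tilted towards benefit. The documents support that for the game route alone; step 5 shows that the net direction is open.
- *Exclusion for short play is inferred.* This stands in part. No passage says that short play disqualifies a child, and Table 1 marks the intervention only in the pre-vaccination column, so it could be judged complete before the needle. Against that, the table does list it as a procedure, the delivery section sets a minimum after vaccination, and SAP 8.1 names an Electronic Game Form. Both readings are open, and staff who know the arm would have to choose.
- *The numbers must be small.* Largely stands. One symptom rated at the lowest positive level makes a case, and few such children need stop a game within a minute. Syncope itself is put at 1.3 to 5 per 1000 in Protocol 1.1, at most 160 × 0.005 = 0.8 child per arm. Shares of 25% or 50% would give two-sided error of 18.3% or 64.7%, but nothing in the documents supports shares of that size.
- *mITT already protects the comparison, and the flow chart would show unequal exclusion.* mITT does keep every such case. But SAP 7.2 promises only counts by arm, not reasons or case status, and the plan does not say that mITT decides.

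**Conclusion.** The point holds in a limited form. The per-protocol rule allows exclusion because of the outcome, through missed assessments in either arm and through early game stopping in the intervention arm only. The second route alone favours the intervention; the net bias could go either way. Its size is unknown and probably small. At an assumed loss of 5% to 10% of intervention cases, with 25% in both arms and 160 per arm, the false-benefit chance is 3.9% to 5.9% against a nominal 2.5%.

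A reader might go further and conclude that the trial's primary result or its 82% power is compromised. The documents do not support that: mITT has no completion rule and is always run. The matter is worth correcting because the per-protocol test answers the primary question at the same alpha, neither population is named as decisive, and the present wording, read literally, excludes children for having the event.

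**What to change.** 1. In SAP 5.2 and section 6, and in Protocol 8.2.1, name mITT as the population that decides the primary objective and per-protocol as supportive.
2. In SAP 6.2 and Protocol 8.2.1, define per-protocol delivery by what happens up to vaccination: assigned device placed and game started in the intervention arm, neither in control. State that stopping the game or device, or missing a later assessment, because of symptoms or signs of presyncope or syncope is not a ground for exclusion in either arm when the primary outcome is known.
3. Fix the list of disqualifying violations before the outcome is tabulated, apply it from delivery records, and report per-protocol exclusions by arm, reason and case status.

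Two features matter. Judging delivery up to vaccination means that nobody needs to know why a child later stopped playing, so delivery can be classified without outcome data. Covering missed assessments in both arms avoids replacing one asymmetry with its opposite. The reason for a missed assessment does have to be recorded.

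The cost is a few sentences in each document and one extra table. The per-protocol set will keep a few children with incomplete game exposure or incomplete secondary assessments, so it is a slightly less strict as-delivered set. Children who miss an assessment for other reasons still leave, which is why exclusions should be shown by case status.

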## 7 Baseline data and flow chart

### 7.1 Presentation of Baseline Data

The following baseline information will be presented by treatment group: age, ethnicity, race, insurance status, fatigue, hunger, thirst, needle fear and phobia, and a generalized anxiety rating scale score, syncope history. Continuous variables will be summarized with standard descriptive statistics including

means, medians, 95% CI, and standard deviations. Categorical variables will be summarized with frequencies and percentages. Ninety-five percent confidence intervals will be provided for descriptive statistics, as warranted. These descriptive statistics will be presented for the mITT and Per-Protocol populations.

